#### **4.7.2 Pharmacodynamic Parameters**

Endpoints for the PD parameter, WBCT, will be calculated for observed and percent-of-baseline values using actual times relative to the end of injection of study drug (ciraparantag or placebo) dose using Phoenix® WinNonlin® 6.3 or SAS® Version 9.4 (SAS Institute, Inc., Cary, North Carolina). All PD endpoints will be derived over the time window from the study drug administration (0 hour) to the last collection time (i.e., 24 hours after the final administration of the study drug).

Triplet WBCT that will be done pre-rivaroxaban, post-rivaroxaban at 3.75 hrs and post-study drug or placebo at 1 hr, will be used for analyzing the inter-observer variability of WBCT by an ANOVA model with effects for observer and subject. The inter-observer variability will be summarized by treatment and time point.

The following endpoints will be calculated for the PD parameters, WBCT:

- $E_{min}$ : minimum value over the 2-minute to 24-hour interval
- $tE_{min}$ : time of  $E_{min}$
- $E_{min(0-6h)}$ : minimum value over the 2-minute to 6-hour interval post-final dose
- $tE_{min(0-6h)}$ : time of  $E_{min(0-6h)}$

- $E_{\max}$ : maximum value over the 2-minute to 24-hour interval
- $tE_{\max}$ : time of  $E_{\max}$
- $\Delta E_{\max}$ : maximum value minus the baseline value (observed only)

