6.8 Efficacy Assessments

Time 0 for all PK and PD assessments will be the end of the study drug injection. Where timing for assessments coincide, PD assessment(s) should be performed first, followed by PK assessment(s), and then ECGs, and vital signs will be performed. The tolerance window to complete PK and PD draws is as follow:

PK/PD Draw Tolerance Window

Sampling Time Point	Tolerance Window
Pre-dose	-60 minutes to 0 hour
>0 hour - 24 hour	-10 minutes to +10 minutes

Over the course of the study, the total estimated volume of blood to be sampled from each subjects for the combined PK, PD and safety evaluations is approximately 225 mL.

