9.7 Pharmacodynamic Analyses

The contract research organization's (██████████) SOPs and Work Instructions will be used as the default methodology if not otherwise specified. All PD computations will be performed using Phoenix® WinNonlin® 6.3, or SAS® Version 9.2 (SAS Institute, Inc., Cary, North Carolina). Graphics will be prepared with SAS® Version 9.2 or SigmaPlot® 12.5. Actual times will be used in the PD analyses.

The PD endpoint will be WBCT.

PD endpoint will be summarized at observed time points and change and/or ratio from baseline values using descriptive statistics and graphical presentations.

Data handling for PD measurements below the limit of quantitation (BLQ) will be specified in the SAP. In the actual analysis, BLQ values will be set to the lower limit of quantitation (LLOQ) for PD data summaries and calculations.

Change-from-baseline and percent-of-baseline will be calculated for all PD endpoints. Baseline for all PD endpoints will be defined as the pre-rivaroxaban sample (approximately four hours before PER977 or placebo administration on Day 3).

The anticoagulant effect of rivaroxaban will be evaluated by comparing WBCT measured at pre-PER977 (about four hours post-rivaroxaban on Day 3) versus baseline (pre-rivaroxaban on Day 3). For the purposes of the PD analyses, subjects with percent-of-baseline WBCT at pre-PER977 $<125\%$ (i.e., $<25\%$ increase) will be considered as rivaroxaban in non-responders and excluded from all PD summaries and assessments.

Listings of individual PD variable collection times, as well as derived sampling time deviations (where applicable), will be provided.

Individual observed and baseline-adjusted values at scheduled time points and PD parameters will be listed and summarized by treatment. In addition, the nature of reversal of anticoagulation (no effect, partial reversal, complete or complete and sustained) based on the definition of reversal of anticoagulation below using WBCT will be listed for each subject and summarized.

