9.9 Pharmacodynamic Parameters

Pharmacodynamic parameters will be calculated for observed and percent-of-baseline values using actual times relative to the start of injection of first study drug (PER977 or placebo) dose using Phoenix® WinNonlin® 6.3 or SAS® Version 9.2 (SAS Institute, Inc., Cary, North Carolina). All PD parameters will be derived over the time window from the first study drug administration (zero hour) to the last collection (i.e., 24 hours after the final administration of the study drug).

The following PD parameters will be determined for the endpoint WBCT:

- E_{min} : minimum value over the two minute to 24 hour interval
- tE_{min} : time of E_{min}
- $E_{min(0-6h)}$: minimum value over the two minute to six hour interval post-final dose
- $tE_{min(0-6h)}$: time of $E_{min(0-6h)}$
- E_{max} : maximum value over the two minute to 24 hour interval
- tE_{max} : time of E_{max}
- ΔE_{max} : maximum value minus the baseline value (observed only)

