#### Definition of Reversal of Anticoagulation

- Complete reversal is achieved for a treatment group if the mean WBCT is  $\leq 110\%$  of baseline at any post-baseline time point up to and including 1 hour following test

article administration. Complete reversal is achieved for a subject if WBCT is  $\leq 110\%$  of baseline at any post-baseline time point up to and including 1 hour following test article administration

- Complete and sustained reversal of anti-coagulation is achieved for a treatment group if the mean WBCT is  $\leq 115\%$  of baseline at all time points between 1 and 8 hours (inclusive) following test article administration. Complete and sustained reversal of anti-coagulation is achieved for a subject if WBCT is  $\leq 115\%$  of baseline at all time points between 1 and 8 hours (inclusive) following test article administration.

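### Emin(0-6h) is cut at exactly 6 hours on actual draw times, so on-schedule 6 h readings count or drop out by chance; minor, and fixed by one windowing rule

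*SAP*

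**What the plan says.** SAP 4.7.2 states that the WBCT parameters "will be calculated for observed and percent-of-baseline values using actual times relative to the end of injection of study drug". It defines Emin(0-6h) as the "minimum value over the 2-minute to 6-hour interval post-final dose", with tEmin(0-6h) as the time of that value. The full-interval Emin is the "minimum value over the 2-minute to 24-hour interval". The same section adds: "All PD endpoints will be derived over the time window from the study drug administration (0 hour) to the last collection time".

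SAP 3 and protocol 6.8.2 schedule post-study-drug WBCT draws at 0.25, 0.5, 0.75, 1, 2, 4, 6, 8 and 24 h. Protocol 6.8 allows 10 minutes either side for every PK or PD draw after time 0 up to 24 h. Protocol 9.7 says: "Actual times will be used in the PD analyses". SAP 4.7.1 and protocol 9.7 provide listings of sampling-time deviations. Neither document says how a draw that is early or late, but within tolerance, is assigned to an analysis window.

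SAP 3.1.1 names Emin(0-6h) and tEmin(0-6h) under the efficacy endpoints.

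**The concern.** A window that ends at 6 hours, a draw scheduled at 6 hours, and a clock that runs on actual time do not fit together. Two subjects who both follow the protocol can be scored over different sets of readings: one on seven draws (15 min to 6 h), the other on six (15 min to 4 h). The difference reflects only the minute at which blood was drawn.

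The effect need not cancel between arms. Removing a reading cannot lower a minimum. It raises the minimum most where WBCT is still coming down, because there the last reading tends to be the lowest. If that describes placebo and not the reversed arms, the active-placebo difference in Emin(0-6h) is overstated in the drug's favour, and tEmin(0-6h) is pulled earlier, more so in placebo.

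**Working it through.** The documents give no figure on this point, so there is nothing of the plan's own to reproduce.

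**1. Which draws meet the limit.** Of the nine scheduled times, only the 6 h draw sits on the edge of the 0-6 h window. The 4 h draw (latest 4:10) is always in and the 8 h draw (earliest 7:50) is always out. A compliant 6 h draw may fall anywhere from 5:50 to 6:10.

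**2. Share of compliant 6 h draws lost.** Take timing errors uniform between *lo* and *hi* minutes (assumed; the documents give no distribution). The share later than 6 h is hi / (hi − lo). The design has 4 × 12 = 48 active and 4 × 4 = 16 placebo subjects.

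| Assumed error (min) | Share lost | Active, of 48 | Placebo, of 16 |
|---|---|---|---|
| −10 to +10 | 10/20 = 50% | 24 | 8 |
| −10 to +5 | 5/15 = 33% | 16 | 5.3 |
| −5 to +10 | 10/15 = 67% | 32 | 10.7 |

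If draws always ran late, all would be lost.

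**3. Effect in a subject who loses the 6 h reading.** This was simulated with 200,000 records per scenario, comparing the minimum with and without the 6 h value. All inputs are assumptions: single-reading CV 5%, with 0.67 of that for the 1 h triplicate median.

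- Placebo = 100 + excess × 0.5^(t / half-life), excess 30% to 60%, half-life 5 to 9 h: Emin(0-6h) rises by 2.7 points (30%, 9 h) to 8.5 points (60%, 5 h).
- Fully reversed, flat at 100%: rises by 0.5 points.
- Placebo back at baseline by 1.5 h: rises by 1.4 points.
- Varying the CV from 3% to 8% gives 2.6 to 8.5 points for slow-decay placebo and 0.3 to 0.7 for full reversal.

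**4. Effect on the arm mean.** Multiply by the 50% share lost:

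- Slow-decay placebo: 0.5 × 2.7 ≈ 1.4, to 0.5 × 8.5 ≈ 4.2 points.
- Full reversal: 0.5 × 0.5, about 0.2 points.
- Placebo at baseline by 1.5 h: 0.5 × 1.4 = 0.7 points.

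The active-placebo gap is therefore inflated by about 1.4 − 0.2 = 1.2 to 4.2 − 0.2 = 4.0 points under slow decay, and by about 0.7 − 0.2 = 0.5 points under early return.

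**5. Cross-check with different curves.** Two other assumed curves were run with a residual SD of 4 or 8 points and errors uniform on ±10 minutes.

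- Placebo falling from 138% at 15 min to 115% at 6 h: the arm mean rises by 3.5 (SD 4) or 3.3 (SD 8) points, and Emin(0-6h) changes in 45% or 34% of subjects. The mean scheduled time of the minimum moves from 5.8 to 4.8 h, or from 5.1 to 4.1 h.
- Reversed arm drifting from 112% to 105%: the arm mean rises by 0.5 or 0.7 points, and the value changes in 17% or 12% of subjects.

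The direction is the same and the placebo shift lies inside the range in step 4. The reversed arm moves slightly more than in step 4 because this curve still drifts down.

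**6. What the protocol's earlier data say about placebo.** They are mixed. After edoxaban (protocol 1.2.4), placebo WBCT reached baseline 1 to 1.5 h after study drug. After enoxaparin (protocol 1.2.3), every placebo subject was classed as only partially reversed over 1 to 6 h, that is, above 120% of baseline. Neither study used rivaroxaban.

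**The case against.** The strongest reply is that little depends on this parameter. The specified treatment-versus-placebo comparison (SAP 4.7.1) is at 15, 30, 45 minutes or 1 hour. No named test, success criterion or dose rule refers to Emin(0-6h), and the full-interval Emin keeps the 6 h draw. Sampling-time deviations are listed, so a reader could see the effect. This stands, and it limits the severity.

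A second reply is that protocol 9.7 makes the contract research organization's procedures the default where nothing else is specified, and those may hold a windowing rule. That is possible, but the SAP does specify actual times here, so a default would not clearly apply.

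Two stronger readings are tempting and are not supported.

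- **Reversal criteria.** A reader might infer from protocol 9.7 that actual times also govern the 1 h and 8 h limits, so that late 8 h draws are ignored and sustained reversal is over-called. The criterion is to be met "at all time points between 1 and 8 hours (inclusive) following test article administration", and it is defined first for a group mean, which presupposes scheduled times. SAP 4.7.1 and protocol 9.7 both list and summarise values at scheduled times. The actual-time sentence in SAP 4.7.2 concerns the PD parameters.
- **Loss of nearly every 6 h draw.** Protocol 9.9 runs the clock "using actual times relative to the start of injection of first study drug", and with an injection of at least 10 minutes that would put a 6 h draw at or beyond 6 h. But SAP 3.1 and 4.7.2 and protocol 6.8 and 7 all set time 0 at the end of injection. Protocol 9.9 is a separate inconsistency and does not measure this one.

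**Conclusion.** The point holds for Emin(0-6h) and tEmin(0-6h) only. As written, the SAP applies actual times to a hard limit that coincides with a scheduled draw, and no rule protects draws within tolerance. About half of the 6 h readings are lost if timing errors are symmetric, and a third to two thirds under moderately skewed errors.

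The resulting bias is conditional. The placebo-arm mean rises by roughly 1.4 to 4.2 points if WBCT decays slowly, or about 0.7 points if it is back at baseline by 1.5 h, against about 0.2 points in a fully reversed arm. These sizes rest on assumed curves, variability and timing errors that the documents do not give. Which placebo pattern rivaroxaban will produce cannot be settled from the protocol.

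Severity is minor: a derived parameter reported under efficacy may be distorted, but no planned test or decision rule is tied to it. For the reversal criteria, scheduled time points are already the natural reading, and no over-calling of sustained reversal should be claimed.

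**What to change.** Add to SAP 4.7.2:

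- Membership of the Emin(0-6h) window is decided by scheduled time point for every draw within the protocol tolerance, so that Emin(0-6h) and tEmin(0-6h) use the 15 min to 6 h samples. The same rule can cover the 24 h draw for the full-interval parameters.
- A stated rule for draws outside tolerance, fixed before the data are analysed.
- Actual time from the end of injection is used only as the reported value of tEmin, tEmin(0-6h) and tEmax.

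The same text can confirm that the reversal criteria in SAP 4.7.1 are scored at scheduled time points. The start-of-injection clock in protocol 9.9 should be reconciled with the end-of-injection time 0 as a separate item.

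The cost is a few sentences in the SAP and a small programming change. No new data are needed.

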## 4.8 Safety Analysis

Safety evaluations will be based on the incidence, intensity, and relatedness of AEs, physical examination findings, ECG parameters, clinical laboratory tests, and vital signs. All summaries will include a pooled ciraparantag column in addition to the presentation of the active dose groups and placebo.

Safety variables will be tabulated and presented for all subjects in the Safety Population. Adverse events will be summarized by MedDRA system organ class, preferred term and group; physical examination findings will be listed; and change from baseline in clinical laboratory parameters, and vital signs parameters will be summarized by group.

### 4.8.1 Study Product Exposure

Study drug and rivaroxaban administration will be listed by subject, indicating date and time of drug dose. Study drug diary will be listed for all subjects, as applicable. A summary of the exposure will be presented.

### 4.8.2 Adverse Events

All clinical AEs occurring after the subject signs the informed consent form (ICF) up to the time of the Follow-up phone call, whether observed by the Investigator or reported by the subject, will be captured. All AEs will be coded and classified according to MedDRA (Version 20.0). The relationship to study drug is judged by the investigator as related or not related. Severity is a measure of intensity whereas seriousness is classified by the criteria based on the regulatory definitions (refer to the protocol Section 6.9.5). An AE of severe intensity need not necessarily be classified as serious. AEs occurring after the date and time of the first dose of study drug up to 30 days following the last dose of study drug are considered treatment emergent AEs (TEAEs).

SAEs occurring up to 30 calendar days post treatment should be reported. Any AEs and SAEs that occur after the specified reporting period should also be reported if in the opinion of the investigator, there is a reasonable possibility for a causal association with the study product. The investigator will follow all SAEs until the SAE is resolved, or stabilized (e.g., in the case of persistent impairment), or returned to baseline, if a baseline value is available, or otherwise justified by the investigator in agreement with the sponsor and all relevant data are received.

All TEAEs will be summarized as the number and percentage of subjects by System Organ Class, Preferred Term and treatment. Separate summaries will be created by

severity and by relationship to study drug. If the same AE (preferred term) is reported more than once for the same subject, it will only be counted once in the summary table.

For summary tables by severity and relationship to study drug, if the same AE (preferred term) is reported more than once for the same subject, the highest severity grade or the strongest relationship to treatment will be counted in the summary table.

All AEs will be listed, and a flag will indicate if the AE is non-treatment emergent or treatment emergent.

All serious AEs (SAEs) will be listed, and a flag will indicate if the AE is non-treatment emergent or treatment emergent.

All AEs leading to study discontinuation will be listed by subject.

All AEs leading to death will be displayed by subject.

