3.3 Study Duration and Dates

Expectation of the total duration of the study is approximately 3 months. Individual subject participation is approximately 50 days inclusive of screening and follow-up. Subjects enrolled will spend up to four nights admitted to an in-patient facility.

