6.9 Adverse Events Assessments

All AEs and SAEs will be captured by electronic data capture (EDC).

All AEs occurring after the subject signs the ICF up to the time of the Follow-up phone call, whether observed by the Investigator or reported by the subject, will be captured. If in the opinion of the Investigator or the sponsor, an AE meets the criteria of an SAE it is to be reported. SAEs occurring up to 30 calendar days post treatment should be reported. Any AEs and SAEs that occur after the specified reporting period should also be reported if in the opinion of the investigator, there is a reasonable possibility for a causal association with the study product.

Medical conditions (including laboratory values/vital signs that are out of range) that were diagnosed or known to exist prior to Informed Consent will be recorded as part of medical history. All SAEs are to be reported according to the procedures in Section [6.9.10 SAE Reporting-Procedure for Investigators](#). Report diagnosis as the AE or SAE term; when the diagnosis is unavailable, report signs and symptoms as individual entries of AE or SAE until the diagnosis becomes available. For events that are serious due to hospitalization, the reason for hospitalization must be reported as the serious adverse event (diagnosis or symptom requiring hospitalization). A procedure is not an AE or

SAE, but the reason for the procedure may be an AE or SAE. Pre-planned (prior to signing the Informed Consent Form) procedure or treatment requiring hospitalization for pre-existing conditions which do not worsen in severity should not be reported as SAEs. For deaths, the underlying or immediate cause of death should always be reported as an SAE. In addition, any serious, untoward event that may occur subsequent to the reporting period that the Investigator assesses as related to study drug should also be reported and managed as an SAE.

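### SAP 4.8.2 gives all treatment-emergent AEs a 30-day window, but non-serious AEs are routinely collected for only 4 to 7 days after dosing

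*SAP*

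**What the plan says.** SAP 4.8.2 contains both halves of the mismatch. On collection, it covers "All clinical AEs occurring after the subject signs the informed consent form (ICF) up to the time of the Follow-up phone call". On classification, events after the first dose of study drug and "up to 30 days following the last dose of study drug are considered treatment emergent AEs (TEAEs". The TEAE tables by system organ class, preferred term, severity and relationship are all built on that definition, and SAP 3.1.3 names TEAE incidence first among the safety endpoints.

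Protocol 6.9 has the same collection limit: "All AEs occurring after the subject signs the ICF up to the time of the Follow-up phone call". Its 30-day period is for serious events: "SAEs occurring up to 30 calendar days post treatment should be reported". For anything later than the specified period, AEs and SAEs "should also be reported if in the opinion of the investigator, there is a reasonable possibility for a causal association with the study product"; SAP 4.8.2 repeats this rule. The protocol sets no TEAE window, so the 30 days for AEs in general comes from the SAP alone.

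The schedule (Protocol, Study Procedures, notes k and n, and Section 7.3) has one study drug injection on Day 3 and a telephone call on Day 7-10. Discharge from the study follows that call, and no later contact is scheduled. Protocol 5.5 and SAP 3.2 blind the subjects and the staff who do the coagulation testing, and name no one else.

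**The concern.** A table headed as TEAEs under a 30-day definition will be read as 30-day incidence. For non-serious events, a low count late in that window would partly reflect that nobody was scheduled to ask.

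The table would also mix two entry rules. Before the call, every AE is to be captured. After it, the reporting requirements bring in SAEs, plus non-serious events that the investigator judges possibly related. Late non-serious events would therefore be selected on relatedness before they reach the relationship table. The investigator who makes that selection is not among those stated to be blinded.

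At stake is how the safety summary is described and, to a lesser degree, how evenly late non-serious events enter the ciraparantag and placebo columns. The WBCT analysis is not touched.

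**Working it through.** The plan gives no figure of its own to reproduce. The check is day arithmetic.

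**Inputs**
- Study drug: Day 3, single dose (Protocol, Study Procedures, note k).
- Follow-up call: Day 7 to Day 10 (note n; Protocol 7.3).
- TEAE window: 30 days after the last dose (SAP 4.8.2).
- Subjects who discontinue early: call 3 to 7 days after discharge (Protocol 6.11.1).
- Planned participation: "Individual subject participation is approximately 50 days inclusive of screening and follow-up" (Protocol 3.3).

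**Days of routine AE collection after dosing** = call day − 3. Share of window = days / 30.

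| Call day | Days collected | Share of 30 | Days not collected | Share of 30 |
|---|---|---|---|---|
| 7 | 4 | 13.3% | 26 | 86.7% |
| 8 | 5 | 16.7% | 25 | 83.3% |
| 9 | 6 | 20.0% | 24 | 80.0% |
| 10 | 7 | 23.3% | 23 | 76.7% |

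**Early discontinuation after dosing.** Take discharge on Day 3 or Day 4. The call then falls between Day 3 + 3 = 6 and Day 4 + 7 = 11, which is 3 to 8 days after dosing. That leaves 27/30 = 90% down to 22/30 = 73% of the window without routine collection.

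**Planned participation.** Screening of up to 36 days, plus the check-in day, plus 10 days gives 36 + 1 + 10 = 47 days, in line with the stated 50 or so. Following everyone to Day 3 + 30 = Day 33 would give 36 + 1 + 33 = 70 days. The stated duration fits the call as the last contact.

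**What the label means (illustration only).** The documents give no AE rate over time. Assume a constant background rate of non-serious events and a true 30-day incidence p. The share of subjects with an event within d days is 1 − (1 − p)^(d/30).

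| Assumed p over 30 days | d = 4 | d = 7 |
|---|---|---|
| 10% | 1.4% | 2.4% |
| 20% | 2.9% | 5.1% |
| 30% | 4.6% | 8.0% |

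This shows only that a 4-to-7-day incidence and a 30-day incidence are different quantities. It does not estimate what this trial would miss, because events caused by the drug need not follow a constant rate.

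**The case against.** The case for leaving the text alone has several parts.

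- **The 30 days may be only a classification limit.** SAP 4.8.2 states the collection period in the same paragraph, the tables give subject counts and percentages without person-time, and the limit matches the SAE reporting period. This is fair as to intent. But a table reader sees the TEAE definition, and nothing requires the shorter collection period to appear beside it.
- **Contact does not always end at the call.** A reader might infer that nobody is asked anything after Day 10 and that nothing but serious or related events could ever enter. The documents do not support that. Discharge depends on AEs having resolved to the investigator's satisfaction, unresolved AEs are followed further (Protocol 6.9), and subjects may be asked back (Protocol 7.3). The point holds for scheduled contact and required reporting, not as an absolute.
- **All groups have the same schedule.** This stands. The gap in collection does not itself favour ciraparantag or placebo.
- **The single-blind design affects every relatedness judgement.** This also stands. What the 30-day rule adds is that, after the call, the judgement decides whether a non-serious event must be reported at all, and not only how it is labelled.
- **Late non-serious drug effects seem unlikely.** Protocol 1.2.4 reports mean half-lives of 12.4 to 20.2 minutes for ciraparantag and 0.527 to 1.76 hours for its metabolite. That lowers the likely number of missed events. It also means that the documents offer little reason to claim 30 days for non-serious events.
- **The listings flag every AE.** If onset dates are shown, a careful reader can separate late events. The incidence tables would still not.

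**Conclusion.** The mismatch is real and worth correcting. For non-serious AEs, the stated 30-day window is routinely ascertained for 4 to 7 days (13-23%), and 77-87% of it lies after general collection ends. Later non-serious events are required to be reported only on a relatedness judgement that is not stated to be blinded. The main harm is mislabelled incidence; uneven late entry between groups is a possibility of unknown size.

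Two stronger readings should be resisted. One is that 77-87% of events would be missed: the figure counts calendar days, and without an AE rate over time no undercount can be calculated. The other is that everything after the call belongs outside the TEAE tables. Both documents require SAEs to be reported for 30 days, so removing them would make the safety summary worse.

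The conclusion assumes dosing on Day 3, the call within Day 7-10, and no scheduled contact afterwards, as both documents state.

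**What to change.** Amend SAP 4.8.2 as follows.

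1. Define TEAEs, for AEs in general, as events with onset from study drug administration through the follow-up call.
2. Keep SAEs with onset up to 30 days after study drug in both the SAE and the TEAE summaries. They fall under a reporting requirement and should be presented as such.
3. Add a note to each TEAE table with the two ascertainment periods: all AEs to the call (4 to 7 days after dosing on schedule), and SAEs to 30 days. The note should say that no contact is scheduled after the call.
4. Put non-serious AEs reported after the call in a separate flagged listing, outside the TEAE incidence tables.

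This needs no new data, no added contact with subjects and no protocol amendment, because the protocol sets no TEAE window. The cost is some SAP wording, a table note and one extra listing. The stated window for non-serious events becomes shorter, which looks less favourable but matches what is collected.
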